Study Design	Participants will electronically acknowledge their consent to participate in the study. The study platform (Gorilla Experiment Builder) will randomize each participant to one of four versions of the online grocery store (Lola's Grocery). The participants will complete a shopping task in the store based on an assigned shopping list. After completing the shopping task, the participant will complete a survey in Qualtrics. The survey will ask a series of questions about the red meat products (e.g., thinking about health/environmental harms, perceived healthfulness, perceived cost). Questions will also include standard demographic and health related variables.
Subject Population	Inclusion Criteria
key criteria for Inclusion and Exclusion:	
 1. 18 years old or older 2. Currently reside in the United States

3. Red meat consumer (1 or more times per week)
4. Does at least half of the grocery shopping for their household

Exclusion Criteria

1. Participated in previous studies linked to this study

Number Of Subjects	Approximately 3,144
Study Duration	Each subject's participation will last approximately 20-30 minutes. The entire study is expected to last 3 months.
Study Phases	(1) Screening: screening for eligibility and obtaining consent
Screening	(2) Randomization: Randomly assigning participants to one of four conditions
RCT	(3) Shopping task: Instruct participants to complete shopping task in an online grocery store (Lola's Grocery)
	(4) Survey: Direct participants to a Qualtrics survey measuring perceptions and reactions to red meat warnings and a red meat tax as well as standard demographics.
Statistical And Analytic Plan	We will descriptively report unadjusted values for all primary, secondary, and other outcomes. We will examine differences between each intervention arm and the control. For primary outcomes only, we will also examine the difference between the intervention arms. In exploratory analyses, we will examine whether predetermined participant characteristics moderate the intervention effects on the primary outcomes by fitting a series of regression models, with trial arm, the moderator (specified as dummy variables), and their interaction as predictors.

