After completing the shopping task, participants will complete a Qualtrics survey measuring reactions to and perceptions of red meat as well as standard demographics. Upon completion, participants will receive a pre-specified incentive from Prime Panels. Additionally, prior to entering the store, participants will be informed that 10% of participants will be randomly selected to receive the groceries they select during the shopping task and the remainder of their budget (\$40) in cash. In reality, 10% of participants will be randomly selected to receive a \$40 gift card. This deception is being

used to incentivize participants to select products that they would actually consume in real life.

Study Duration, Enrollment and Number of Subjects

Participation in the study will last approximately 20-30 minutes. The entire study is expected to last three months.

Study Population

Inclusion Criteria

1. 18 years old or older
2. Currently reside in the United States
3. Red meat consumer (1 or more times per week)
4. Does at least half of the grocery shopping for their household

Exclusion Criteria

1. Participation in previous studies linked to this study

STUDY PROCEDURES (what will be done)

Study Steps

Participants will be recruited through Prime Panels, a survey research firm we have worked with previously. If interested, panel members will complete a screener in the Gorilla Experiment Builder to see if they are eligible. If they are not eligible, panel members will be redirected to a termination page indicating they are not eligible to participate. If they are eligible, panel members will be redirected to a consent form. If they agree to the consent form, they will acknowledge their consent by clicking an arrow to proceed to the study.

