Following online consent, participants will be randomized to one of the four arms by Gorilla and enter into Lola's Grocery. In this online grocery store, participants will complete a shopping task. They will be asked to select items using a pre-determined nine-item shopping list (see below), and they will be informed that their budget is \$40. To complete the shopping task, a participant's shopping basket must have +/- 2 items of the total number of items on the shopping list (7-11 items). After completing the shopping task, participants will be redirected to a survey. In the survey, participants will answer standard behavior and reaction measurement questions, as well as standard demographic questions. Prior to the shopping task, participants will be informed that 1 in 10 participants will actually receive, via mail, the groceries they select and the remainder of their shopping budget (\$40). The purpose of this is to incentivize participants to make purchases that reflect their real-life shopping habits. However, in reality, we will send 1 in 10 participants a gift card of \$40 (the shopping task budget). At the end of the survey, we will inform the 1 in 10 participants that the panel vendor will be sending them a gift card

rather than groceries and ask for their email address. The panel vendor will email the gift card.

Shopping List:

1. 1 pizza
2. 1 burrito
3. Burger patties (meat or vegetarian)
4. Breakfast sausages (meat or vegetarian)
5. 1 frozen individual meal
6. 1 loaf of bread
7. 1 sandwich filling (for example, ham, turkey, or peanut butter)
8. 1 pack of tortillas
9. 1 taco filling (for example, steak, chicken, or beans)

Subject Completion/Withdrawal Procedures

A study participant is determined to have completed the study when they have finished and exited the study survey. To withdraw their data from the study, a participant would have to contact the study team or the university IRB.

Screen Failure Procedures

Prior to entering into the study, individuals will complete a survey screener. If the individual is younger than 18 years old, does not live in the United States, does not eat red meat at least one or more times per week, or does not do at least half of the grocery shopping for their household, they will be deemed ineligible. Such participants will be redirected to a screen notifying them that they are ineligible for the study.

SCREENING AND MONITORING EVALUATIONS AND MEASUREMENTS (how measurements will be made)

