This online grocery store felt like a real online grocery store.	1=Strongly disagree 2=Somewhat disagree 3=Neither agree nor disagree 4=Somewhat agree 5=Strongly agree
Say how much you agree or disagree with the following statements.	
Red meat products should be labeled with warnings describing the link between red meat and diseases, such as colon cancer.	1=Strongly disagree 2=Somewhat disagree 3=Neither agree nor disagree 4=Somewhat agree 5=Strongly agree
Red meat products should be labeled with warnings describing the link between red meat and environmental harms.	1=Strongly disagree 2=Somewhat disagree 3=Neither agree nor disagree 4=Somewhat agree 5=Strongly agree

Red meat products should receive an extra tax to reflect the health and environmental harms of red meat consumption.
	
1=Strongly disagree 2=Somewhat disagree 3=Neither agree nor disagree 4=Somewhat agree 5=Strongly agree

---	---

STATISTICAL CONSIDERATION

Statistical Methods

We will descriptively report unadjusted values for primary, secondary, and other outcomes.

We will use a two-sided critical alpha of 0.05 to conduct all statistical tests. Per CONSORT guidelines, we will not test for balance in covariates. Primary analyses will be intent-to-treat, including all eligible participants with non-missing outcome data (e.g., complete-case).

Sensitivity Analyses

We will describe dropout (defined as entering the store but not completing the purchasing task) by study arm and by screener characteristic (age, red meat consumption). If differential dropout is identified, we will consider sensitivity analyses to handle missing outcome data, such as inverse probability weighting.

For all primary, secondary, and other outcomes, we will assess whether the outcomes vary by study arm with regression models, in which the referent group will be the control (compared to each of the three interventional study arms). For the primary outcomes, the regression model will be selected based on the frequency of zero purchases of products containing red meat. If the frequency of zeros is high (>10% of participants), we will consider models to deal with the high proportion of zeros (e.g., zero-inflated Poisson or zero-inflated negative binomial for a count variable; fractional regression for percentage variable). Choice of model will also depend on whether heteroscedasticity exists. Model selection exercises will be reported. For secondary and other outcomes, we will use linear regression.

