The study survey will be programmed to not collect IP addresses. The research study will collect the email of every 10th participant for gift card distribution. However, email will be collected in a separate survey, and a randomly generated id will connect the email survey and study survey. Researchers will store the study data on a remote terminal server, and only research investigators and staff will have access to the data. Participants' emails will be shared with the panel vendor in order to distribute the \$40 gift card, however study staff will not provide the panel vendor with participants' other survey responses. Once gift cards are distributed, participant emails will be deleted.

RECRUITMENT STRATEGY

Participants will be Prime Panels participants who have voluntarily signed up to complete tasks remotely, including research surveys. Our study sample will include only those who self-enroll in the study based on interest, availability, and meeting the inclusion criteria. There is no specific advertisement for this study. Rather, Prime Panels identifies users for the survey based on the inclusion criteria (age 18 or older, resides in United States, consumes red meat at least once a week, and does at least 50% of household grocery shopping) and informs them of the study opportunity.

CONSENT PROCESS

To provide consent, individuals will first complete a survey screener in Qualtrics. If they are eligible for the study, they will be redirected to the study consent form. If the participant agrees to the consent form, they are informed that by continuing to the study, they are consenting to participate. The consent process is completed entirely online, and at no point in the study do participants interact with the study team.

PLANS FOR PUBLICATION

The investigators plan to publish as an open-access peer-reviewed paper. They will target public health peer-reviewed journals for manuscript submission.

REFERENCES

1. World Cancer Research Fund International. WCRF International Food Policy Framework for Healthy Diets: NOURISHING. World Cancer Reserach Fund International. http://www.wcrf.org/policy_public_affairs/nourishing_framework/index.php. Published 2014. Accessed July 20, 2014.

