First, we will conduct a soft launch of 200 participants. With the data from the 200 participants, we will run descriptive analyses of the primary, secondary, and other outcomes, and we will confirm randomization is working properly.

If randomization is working properly and there are not apparent issues with the data collection (e.g. technical issues with the online store software), we will resume data collection until the final sample is achieved. The original 200 participants from the soft launch will be included in the final dataset.

If randomization is not working properly and/or there are apparent issues with the data collection (e.g., erroneous skip patterns), we will address all identified issues then resume data collection until the final sample is achieved. The original 200 participants from the soft launch will not be included in the final dataset.

We will descriptively report unadjusted values for primary, secondary, and other outcomes.

We will use a two-sided critical alpha of 0.05 to conduct all statistical tests. Per CONSORT guidelines, we will not test for balance in covariates. Primary analyses will be intent-to-treat, including all eligible participants with non-missing outcome data (e.g., complete-case).

Sensitivity Analyses

We will describe dropout (defined as entering the store but not completing the purchasing task) by study arm and by screener characteristic (age, red meat consumption). If differential dropout is identified, we will consider sensitivity analyses to handle missing outcome data, such as inverse probability weighting.

For all primary, secondary, and other outcomes, we will assess whether the outcomes vary by study arm with regression models, in which the referent group will be the control (compared to each of the three interventional study arms). For the primary outcomes, the regression model will be selected based on the frequency of zero purchases of products containing red meat. If the frequency of zeros is high (>10% of participants), we will consider models to deal with the high proportion of zeros (e.g., zero-inflated Poisson or zero-inflated negative binomial for a count variable; fractional regression for percentage variable). Choice of model will also depend on whether heteroscedasticity exists. Model selection exercises will be reported. For secondary and other outcomes, we will use linear regression.

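### The primary regressions name no adjustment covariate, although age and red meat consumption are recorded at screening before randomisation, so available precision is left unused

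*SAP*

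**What the plan says.** The inferential model is described under Sensitivity Analyses in the SAP: "we will assess whether the outcomes vary by study arm with regression models, in which the referent group will be the control". The protocol's Statistical Consideration section has the same sentence, beginning "For all primary, secondary, and other outcomes, we will assess whether the outcomes vary by study arm with regression models". Both add a rule for choosing the model family from the share of zeros and from heteroscedasticity, with "zero-inflated Poisson or zero-inflated negative binomial for a count variable; fractional regression for percentage variable" as examples. Neither document lists any predictor other than arm for the primary models, and neither says whether covariates will be used. The nearby statements are that unadjusted values will be reported descriptively and that covariate balance will not be tested. Neither of these settles the question.

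On what is known before randomisation:

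- The SAP describes dropout by arm and "by screener characteristic (age, red meat consumption".
- In the protocol's Study Steps, "panel members will complete a screener in the Gorilla Experiment Builder to see if they are eligible". Consent follows for those who are eligible.
- Then: "Following online consent, participants will be randomized to one of the four arms by Gorilla".
- Screen Failure Procedures make both age and red meat consumption conditions of eligibility.

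Baseline terms appear only in the exploratory moderation models, fitted one moderator at a time. Moderators (a), frequency of red meat intake, and (f), age group, are not said to be the screener items. The synopsis says of the post-task survey: "Questions will also include standard demographic and health related variables".

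**The concern.** A shopper's usual red meat intake may well predict how many red meat products go into the basket, and age may too. If so, leaving these items out of the primary model leaves explainable variation in the error term. The confidence intervals for the arm contrasts are then wider than they need be. The data are already collected, should exist for every randomised participant, and must be linked to arm for the dropout table anyway.

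The second issue is prespecification. Adjustment is neither stated nor excluded, and the model family is itself to be chosen from the data. Naming the covariates and their source now removes one choice that could otherwise be made after the results are seen. The source matters because answers given after the shopping task could be affected by the labels or the tax. Screener answers cannot be.

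**Working it through.** **Inputs from the documents.** Two-sided alpha 0.05 (Statistical Methods); d = 0.1, 80% power, 786 per arm, 3,144 in total, 2 × 2 factorial (Sample Size and Power); equal allocation (protocol, Study Design); each arm against control, plus all pairwise comparisons for the primary outcome (SAP, Statistical Methods).

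**Input not in the documents.** R², the share of outcome variance explained by the two screener items within arm. Assumed values: 0.02, 0.05, 0.10, 0.20.

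**The plan's own figure.** A factorial main effect pools two arms against two. The normal approximation gives 1,570 per pooled level, or 785 per arm. The noncentral F with 1 and 4n − 4 degrees of freedom and f = d/2 = 0.05 gives 786 as the smallest n per arm that reaches 80% (power 0.8003). The stated 786 is therefore reproduced as an unadjusted main effect. Read as a single pairwise contrast, d = 0.1 would need 1,570 per arm.

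**Effect of adjustment (linear model).**

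- Standard error multiplier: √(1 − R²)
- Equivalent extra participants: 3,144 × (1/(1 − R²) − 1)
- Power: noncentral t, 3,140 error df, effective d = d/√(1 − R²), with 1,572 v 1,572 for the main effect and 786 v 786 for a pairwise contrast

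For example, at R² = 0.10 the multiplier is √0.90 = 0.949, a fall of 5.1%. The equivalent extra sample is 3,144 × 0.1111 = 349.

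| R² (assumed) | SE reduction | Equivalent extra participants | Main effect, d = 0.1 | Pairwise, d = 0.1 | Pairwise, d = 0.15 |
|---|---|---|---|---|---|
| 0 | 0 | 0 | 80.0% | 50.9% | 84.4% |
| 0.02 | 1.0% | 64 | 80.8% | 51.7% | 85.1% |
| 0.05 | 2.5% | 165 | 82.0% | 52.9% | 86.2% |
| 0.10 | 5.1% | 349 | 84.0% | 55.1% | 88.0% |
| 0.20 | 10.6% | 786 | 88.0% | 60.1% | 91.4% |

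The value d = 0.15 is illustrative and is not in the documents. At d = 0.25, the sugary-drink warning effect that the plan cites, pairwise power is about 99.9% or higher throughout. An R² of about 0.50 would be needed for 80% pairwise power at d = 0.1.

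**Does the gain carry over to the plan's non-linear models?** This was simulated on assumed data: 600 trials per setting, 786 per arm, a four-level frequency covariate, 15–18% zeros, and baskets of 7–11 items. The estimate was the standardised arm difference in means, and its standard error was the empirical SD across trials.

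| Model | R² | SE reduction, simulated | 1 − √(1 − R²) |
|---|---|---|---|
| Fractional regression (percent) | 0.017 / 0.054 / 0.120 | 0.8% / 2.8% / 6.3% | 0.9% / 2.7% / 6.2% |
| Zero-inflated Poisson (count), covariate in both parts | 0.019 / 0.059 / 0.130 | 0.8% / 3.3% / 7.0% | 1.0% / 3.0% / 6.7% |
| Zero-inflated Poisson, covariate in count part only | 0.019 / 0.059 / 0.130 | 0.6% / 2.8% / 5.7% | – |

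With R² near 0 the change was −0.1%, so there was no material loss. Adjusted and unadjusted mean differences agreed (count at R² = 0.019: −0.137 for both).

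**The case against.** The case against giving this weight is that no defect is alleged. An unadjusted comparison in a randomised trial of 3,144 is legitimate. The plan lists extra predictors where it wants them, in the moderation models, so the natural reading is that the primary models are deliberately arm-only, and a later addition would be a visible departure. The benefit is wholly assumed: no R² is given, item coding is not stated, and the once-a-week criterion restricts the range of red meat consumption. The larger power gains belong to a factorial main effect that the analysis sections do not list. For the listed pairwise contrasts at d = 0.1, power stays near 50–55% for R² up to 0.10. A single sentence declaring the analysis unadjusted would resolve the ambiguity.

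Most of these facts stand. The analysis is unbiased without adjustment, the gain could be close to nothing, and the pairwise shortfall is a separate problem that adjustment does not cure. The simulation stops at R² of 0.13, so the 0.20 row rests on the linear formula alone. Passing the eligibility threshold shows only that each item was asked. Tabulating dropout by the items suggests that finer gradation is kept, but does not prove it.

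None of this is a reason to leave the items out. The cost is negligible even when they are uninformative, and the sample was sized to just 80% on its own basis. A declaration of no adjustment would remove the ambiguity but not recover the precision.

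**Conclusion.** The concern holds. The primary models are specified by arm alone, while two plausibly prognostic items are recorded before randomisation and already needed alongside arm. This is a worthwhile improvement, not a correction of bias.

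Its likely size is modest: standard errors lower by 1.0% to 5.1% for R² from 0.02 to 0.10, and by 10.6% at R² = 0.20. Three assumptions carry this. The screener responses must be kept with some gradation, they must predict the basket, and the linear-model relation must hold approximately in whichever model family is chosen. The simulation supports the last of these for R² up to about 0.13. If either of the first two fails, the change is close to neutral.

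**What to change.** Add a paragraph to the SAP to this effect, before outcomes are compared by arm:

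> The primary models for both co-primary outcomes will include screener red meat consumption (categories as asked) and screener age as covariates. Only screener items recorded before randomisation will be used, not items from the post-task survey. The primary estimate is the adjusted difference in means; the unadjusted difference will be reported alongside. If a zero-inflated model is chosen, arm and both covariates enter the count part and the inflation part. If fractional regression is chosen, they enter the mean model. In either case the standardised (marginal) difference in means will be reported with a robust or bootstrap standard error.

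The standardisation sentence is needed because covariates in a non-linear model can otherwise change the quantity being estimated.

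If the investigators prefer an unadjusted primary analysis, the SAP should say so and prespecify the adjusted model as a supporting analysis. That settles the ambiguity but leaves the precision out of the primary result.

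Two side clarifications belong in the same edit. State whether moderators (a) and (f) are the screener items. State also which platform holds the screener record: Study Steps places the screener in Gorilla, whereas Consent Process says "To provide consent, individuals will first complete a survey screener in Qualtrics".

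The cost is one short paragraph and no new data collection.

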For all analyses, means will be compared between each of the treatment groups and the control group, and for the primary outcome all pairwise comparisons of means will be examined. We will consider a result statistically significant at $p < 0.05$.

In exploratory analyses, we will examine whether the following participant characteristics moderate the intervention effects on the primary outcomes:

- a. Frequency of red meat intake
- b. Interest in health
 - For interest in health, we will take the average of the 3 items if $\alpha > .70$. The 3 items are adapted from Hearty et al. (2006). If α is not above .70, we will either create a scale excluding the item that makes the three-item scale drop below .70, if there is one; or we will look at the items separately.
- c. Interest in sustainability
 - For interest in sustainability, we will take the average of the 6 items if $\alpha > .70$. The six items are adapted from Haws et al. (2014). If α is not above .70, we will either create a scale excluding the item(s) that make(s) the six-item scale drop below .70, if there is one; or we will look at the items separately.
- d. Household income level
- e. Educational attainment

- f. Age group
- g. Race/ethnicity
- h. Political orientation
- i. Gender

To test whether these characteristics moderate the effect of the intervention on the count or percentage of products containing red meat selected, we will fit a series of regression models (one for each potential moderator), with trial arm, the moderator (specified as dummy variables), and their interaction as predictors. We will use a Wald chunk test to determine the joint interaction. We will quantitatively evaluate the presence of moderation by calculating the marginal effect of the intervention on the outcome at different levels of the moderating variable. If the pattern of main results is similar between intervention arms (warning label, tax, and warning plus tax), we will consider combining intervention arms for the moderation analysis.

Sample Size and Power

Sample size calculations were conducted using PASS 2019 Power Analysis and Sample Size Software (NCSS, Kaysville, Utah, USA). The effect size for the warning label was hypothesized to be the smallest effect size, and so the sample size was chosen to power this effect. With this sample size, the power associated with the tax and combined conditions will be maintained at approximately the same level or higher (better).

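### Must the SAP change because it does not say when the health-interest and sustainability-interest moderators are asked?

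*SAP*

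**What the plan says.** In its exploratory analyses the SAP states that "we will examine whether the following participant characteristics moderate the intervention effects on the primary outcomes" and lists nine characteristics. Two are attitude scales with scoring rules: "For interest in health, we will take the average of the 3 items" and "For interest in sustainability, we will take the average of the 6 items", each subject to a reliability threshold. Each moderator gets its own model with arm, moderator dummies and their interaction, a joint Wald test, and an assessment made by "calculating the marginal effect of the intervention on the outcome at different levels of the moderating variable". The Protocol's Statistical Methods section says the same. Neither gives a time of measurement for the nine items.

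The order of events is in the Protocol, Study Steps. First, "panel members will complete a screener in the Gorilla Experiment Builder to see if they are eligible". Then, "Following online consent, participants will be randomized to one of the four arms by Gorilla", and they enter the store. Finally, "After completing the shopping task, participants will be redirected to a survey". The Protocol synopsis places demographic and health-related questions in that last survey.

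Under Sensitivity Analyses the SAP describes dropout "by study arm and by screener characteristic (age, red meat consumption"). Under Statistical Methods it rules out balance tests on covariates. It plans no comparison of the two interest scales by arm.

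**The concern.** A moderator should be something the intervention cannot alter. Read literally, the sequence has no baseline questionnaire between consent and the store, so the nine items seem to belong in the survey after shopping. By then two arms have seen warnings about cancer and the environment, the same domains as the two scales, and two arms have faced a 30% tax. The SAP itself expects arm effects on neighbouring beliefs in that survey, such as perceived cancer risk and perceived environmental harm.

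If exposure moves the answers, people at the same observed scale level are no longer comparable across arms. The effects by level would then be biased, and an uneven shift could produce a gradient where no moderation exists. The ban on balance testing is sound for variables fixed before randomisation, but it gives no reason to skip a look by arm at variables measured afterwards. At stake is a misleading statement about who responds to warnings.

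**Working it through.** **The plan's own figure.** For d = 0.1, two-sided alpha 0.05 and 80% power, n per factor level = 2 × (1.960 + 0.842)² / 0.1² ≈ 1,570, or 785 per cell. The exact F test for a main effect in a 2 × 2 design has power 0.7998 at 785 and 0.8003 at 786 per cell. The stated 786 per arm (3,144 in total) therefore reproduces, and this point does not affect it.

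**Is timing after the store established?** Three lists might seem to settle it, and none is an inventory.
- Protocol, Screen Failure Procedures, gives the answers that disqualify. It does not claim to give every screener question.
- The SAP's dropout sentence names two screener characteristics. The screener also asks about US residence and share of grocery shopping, so that parenthesis is incomplete.
- The Protocol's measures table omits the nine items, but also omits the intention outcome (SAP outcome M) and all demographics.

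The platform does not help either: Study Steps puts the screener in Gorilla, and Consent Process puts it in Qualtrics. The survey after the store is the likelier place, but the documents do not fix it.

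**How large could the harm be?** The documents give no inputs, so these are assumptions: outcome and scale in SD units, true effect -0.10 at every level, scale-outcome slope b = -0.2, exposure shifting the scale by s, and levels taken as thirds of the observed scale.

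At a fixed observed level, an exposed person's underlying interest is lower by s. The apparent effect there is -0.10 - b × s, that is -0.08, -0.06 and -0.04 for s = 0.1, 0.2 and 0.3. Thirds are wide, so the bias is slightly smaller:

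| Uniform shift s | Effect within thirds | Bias |
|---|---|---|
| 0.1 | -0.081 to -0.086 | 0.014 to 0.019 |
| 0.2 | -0.062 to -0.071 | 0.029 to 0.038 |
| 0.3 | -0.044 to -0.057 | 0.043 to 0.056 |
| -0.2 | -0.129 to -0.138 | -0.029 to -0.038 |

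The last row shows that the direction reverses if exposure lowers interest.

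**Against precision.** A third of 786 is 262 per arm. SE = √(2/262) = 0.087, so the 95% half-width is 1.96 × 0.087 = 0.17 SD. The bias for positive shifts is 0.014/0.087 = 0.16 to 0.056/0.087 = 0.64 standard errors.

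**Harsher settings.** Over slopes -0.1 to -0.3 the bias for the same positive shifts runs from 0.007 to 0.085 SD. If only people below the mean shift (average 0.2 SD, b = -0.2), the effects from lowest to highest third are -0.042, -0.063 and -0.100. The joint interaction test (2 df, 786 per arm, 8,000 simulated trials) rejects in 4.8 to 5.4% of trials under uniform shifts. Under the uneven shift it rejects in 7.1%, or 9.0% at b = -0.3. The most extreme case examined had a scale-outcome correlation of -0.4, a mean shift of 0.2 SD, and low-interest people moving more. It gave +0.01 in the lowest third and -0.07 in the highest, with 9.5% rejection (1,000 trials).

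**What would a check by arm show?** At 786 per arm the half-width is 1.96 × √(2/786) = 0.099 SD, and power for a 0.1 SD shift is Φ(0.1/0.0504 - 1.96) = 51%. Both warning arms against both others (1,572 each) give 0.070 SD and 80%, but that contrast would miss a shift caused by the tax.

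**The case for a change.** The strongest reply is that the remedy costs almost nothing: one sentence on timing and two regressions on data already collected. The SAP is specific about scoring these scales, so silence on when they are asked is odd. The quantity most exposed to bias, the effect by level, is also the one the SAP says it will use to judge moderation.

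Much of this stands. Timing is not stated, the survey after the store is the natural reading, no look by arm is planned, and a false gradient is possible under an uneven shift of sufficient size.

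What does not follow is that the plan gives a wrong answer. If the items precede the store, nothing needs altering. If they follow it, what is needed is a caveat on two exploratory results, and that caveat depends on timing, not on what the check shows. A null check could not exclude small shifts, and at 51% power it would often miss a 0.1 SD shift between two arms. Moving the items ahead of the store is no clear gain either: questions on health and sustainability just before shopping could prime every arm and disturb the co-primary outcomes. Asking them afterwards would be a fair trade-off.

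**Conclusion.** No change to the plan. The gap is real but small: an unstated time of measurement for two of nine exploratory moderators. It is a fact of the programmed questionnaire that the analysts will know and can report with the results. Harm needs two things the documents do not establish: that the items follow the store, and that exposure moves general interest in health or sustainability. The SAP's psychological hypotheses concern beliefs about red meat and its products, thoughts while shopping, and intention to eat less of it; none concerns general interest. The assumed shifts equal or exceed, by up to three times, the d of 0.1 on which the trial is powered.

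At an assumed slope of -0.2 and uniform positive shifts of 0.1 to 0.3 SD, the bias is at most 0.056 SD, about a third of the 0.17 SD half-width of a single stratum effect, and its sign is not known in advance. Stronger slopes combined with uneven shifts would be worse, exceeding one standard error in the most extreme case examined, but nothing in the documents points to them. The co-primary arm comparisons do not depend on these scales, and the other seven moderators are not in question here.
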